	3.2 Audits and inspections	
	3.3 Disclosure of Data	
14	STUDY MANAGEMENT	33
15	PUBLICATION AND DISSEMINATION	33
16	REFERENCES	34

1 LIST OF ABBREVIATIONS and TERMS

AE Adverse event

ARSAC Administration of Radioactive Substances Advisory

Committee

CT Computed Tomography

ED Effective Dose (i.e., the sum of risk weighted organ absorbed

radiation dose used as a measure of stochastic radiation

risk)

EC Ethics committee

FDG ¹⁸F – fluorodeoxyglucose

¹⁸F Fluorine with an Atomic Mass of 18

[¹⁸F]FPIA ¹⁸F-fluoropivalate (¹⁸F-fluoro-2,2-dimethylpropionic acid)

GCP Good Clinical Practice

GMP Good Manufacturing Practice

i.v Intravenous MBq Megabecquerel

PET Positron emission tomography

SAE Serious adverse event
SRS Stereotactic radiosurgery
SUV Standardized uptake value
MRI Magnetic resonance imaging

eGFR Estimated glomerular filtration rate

2 SYNOPSIS

Name of Sponsor: Imperial College London

Name of biomarker: [18F]Fluoropivalate positron emission tomography magnetic resonance imaging (18F-FPIA PET/MRI)

Title of Study: Determining the magnitude of early steps of fatty acid oxidation in cerebral metastases using [18F]FPIA PET/MRI

Study Centres:

- Invicro, Hammersmith Hospital Campus, UK
- Imperial College London
- Imperial College Healthcare NHS Trust, London

Phase of Development: Explorative biomarker use/ Phase 2

Primary Objective:

• Determine the magnitude of the early steps of fatty acid oxidation in cerebral metastases using [18F]FPIA PET/MRI.

Secondary objective:

 Investigate the magnitude of tracer-derived biochemical uptake between treated metastases and treatment naïve metastases.

Tertiary objective:

 Comparison of tracer-derived biochemical uptake measure with conventional MRI variables including perfusion imaging and contrast enhancement.

Primary Endpoint:

• Quantitative measurement of [18F]FPIA uptake in cerebral metastases.

Secondary endpoint:

• Distribution of [18F]FPIA uptake in lesions which have undergone treatment, with those that are treatment naïve.

Tertiary endpoint:

• Correlation of [18F]FPIA variables with volumetric and functional MRI variables including perfusion.

Selection of Subjects: Inclusion Criteria:

Patients with radiological evidence of cerebral metastases on MRI that are either:

A) Treatment naïve*

or

- B) SRS +/- combination treated** and
- C) that fulfill the following criteria:
- 1. Age ≥18
- 2. Target metastases size ≥ 1cm.
- 3. WHO performance status 0 2.
- 4. If female, the subject is either post-menopausal (at least 1 year), or surgically sterilized (has had a documented bilateral oophorectomy and/or documented hysterectomy for at least 2 years), or if of childbearing potential, must have a negative urine beta human chorionic gonadotropin (β-HCG) pregnancy test done prior to tracer administration.
- 5. The subject is able and willing to comply with study procedures, and a signed and dated informed consent is obtained.
- 6. The subject has a satisfactory medical history as judged by the investigator with no significant co-morbidities.
- 7. The subject's clinical and laboratory tests are within normal limits and/or considered clinically insignificant.
- * Treatment Naïve = = patients who have not and will not be undergoing treatment for cerebral metastases at the time of the PET/MRI scan.
- ** SRS+/- combination therapy = patients who have completed the stereotactic radiosurgery (SRS) part of a combination regime enabling a 4-8 week post SRS treatment PET/MRI scan. Combination therapy can be +/-chemotherapy/immunotherapy/targeted therapies.

Exclusion Criteria:

- 1. The subject is pregnant or lactating.
- 2. Any other chronic illness that will or musculoskeletal condition that would not allow comfortable performance of a PET study.
- 3. Prior use within 14 days of enrolment or concurrent therapy with any other investigational agent.
- 4. Unsatisfactory renal function (eGFR<30).

5. The subject has non-MRI compatible devices (e.g. a pacemaker, an implantable cardioverter-defibrillator (ICD), a nerve stimulator, a cochlear implant or a drug pump) or implanted material (e.g. non-MRI compatible sternal wires, biostimulators, metals or alloys).

Number of Patients Planned: 24

• In the event of withdrawals or unevaluable data, additional patients will be recruited to reach a total number of 24 evaluable subjects.

Treatment of Subjects: Experimental imaging biomarker tracer:

Subjects will receive a single I.V. bolus injection of [¹⁸F]FPIA over a period of about 30 seconds. The tracer injection will be followed by a saline flush. Patients will receive a maximum ¹⁸F activity of 370 MBq per scan, and a maximum of 2 scans.

Statistical Methods and Planned Analysis:

• The study is an Observational Non-randomised Phase 2 study to determine the magnitude of the early steps of fatty acid oxidation in cerebral metastases using [¹8F]FPIA PET/MRI. This is the first time we are using FPIA in patients with cerebral metastases, thus we do not know *a priori* the magnitude of uptake. Statistical tests will use a 0.05 significance level and will be 2-sided unless otherwise noted. 24 evaluable patients will be recruited for the study with the Upper Confidence Interval of sensitivity to detect fatty acid metabolism set to ≥ 90%.

3 BACKGROUND AND RATIONALE

3.1 Background

Cerebral metastases represent a significant problem for oncological management. It is estimated that 20% to 40% of patients with cancer will develop metastatic cancer to the brain during the course of their illness [1]. The burden of brain metastases impacts on quality and length of survival. Although cerebral metastases may spread from any primary site, most common primary site is the lung, followed by the breast then gastrointestinal sites. Very recent work indicates a striking common metabolic phenotype of brain metastases and glioblastoma to simultaneously oxidise acetate and glucose [3]. This adaptation may be important for meeting the high biosynthetic and bioenergetic demands of malignant growth. Furthermore, it has been shown that the key gene responsible FPIA METS_PROTOCOL_V2.0_08APR2022

for this phenotype, ACSS2, permits cells to exist under bioenergetic stress, which is a potential adaptation to therapy resistance [4]. Tumour cells, including brain tumour cells efficiently oxidize fatty acids synthesized from acetate to generate a substantial part of the cell's ATP requirement, as well as NADPH to buffer reactive oxygen species.

There is currently no method for quantifying tissue fatty acid oxidation in humans. Our group has characterized ¹⁸F-fluoropivalate ([¹⁸F]FPIA; 3-¹⁸F-fluoro-2,2-dimethylpropionic acid) as a tracer to report the early steps of fatty acid oxidation in non-clinical studies using PET imaging [4] [5]. ¹⁸F-FPIA shows high contrast for imaging brain tumour xenografts implanted subcutaneously in mice [5], and orthotopically in the brain (unpublished) with the magnitude of tumour uptake equivalent to that of conventional tracers such as [¹⁸F]FDG but with significantly lower normal brain uptake giving a high signal to noise ratio enabling its use as suitable surrogate biomarker for fatty acid oxidation. Our current objective is to quantify the magnitude of early step fatty acid oxidation in cerebral metastases thought to possess enhanced fatty acid oxidation [3].

Combined hybrid PET/MRI technology permits simultaneous acquisition of PET imaging with conventional MRI sequences including T1, T2/FLAIR (with and without contrast) and perfusion (DSC-MRI). Patients with brain metastases will either be treatment naïve or have undergone radiotherapy and so we will have the opportunity to investigate the degree of fatty acid oxidation between untreated and treated patient groups, as well as differences in fatty acid metabolism between cerebral metastases from different primary tumours. Depending on the outcome of this study, [18F]FPIA PET/MRI may be further investigated, in a longitudinal setting, for assessing response to therapies including intracranial stereotactic radiosurgery in patients with brain metastases.

3.2 Rationale

3.2.1 Aim

The aim of this study is to quantify the degree of early step fatty acid oxidation in cerebral metastases as imaged by [18F]FPIA PET/MRI.

3.2.2 Hypothesis

We hypothesise that FPIA uptake will be higher in metastases that are treatment naïve compared to those that have undergone treatment, in keeping with viable tumour cells having a high propensity to generate ATP and NADPH via fatty acid oxidation under bioenergetic stress.

4 STUDY OBJECTIVES AND ENDPOINTS

4.1 Study Objectives

4.1.1 Primary Objective:

 Determine the magnitude of the early steps of fatty acid oxidation in cerebral metastases using [¹⁸F]FPIA PET/MRI.

4.1.2 Secondary Objectives:

 Investigate of the magnitude of tracer-derived biochemical uptake between treated metastases and treatment naïve metastases.

4.1.3 Tertiary Objective:

 Comparison of tracer-derived biochemical uptake measure with conventional MRI variables including perfusion imaging and contrast enhancement.

4.2 Study Endpoints

4.2.1 Primary Endpoint:

• Quantitative measurement of [18F]FPIA uptake in cerebral metastases.

4.2.2 Secondary Endpoints:

• Distribution of [18F]FPIA uptake in lesions which have undergone treatment, with those that are treatment naïve.

4.2.3 Tertiary Endpoint:

[figure not shown]
• Correlation of [¹⁸F]FPIA variables with volumetric and functional MRI variables including perfusion.

5 STUDY OUTLINE

5.1 Study Overview

24 evaluable patients with radiological evidence of cerebral metastases on MRI will be enrolled into the study (12 who are treatment naïve + 12 who have completed SRS+/- combination therapy). The patients invited to participate in the study will provide written informed consent, but will only undergo [¹8F]FPIA PET/MRI imaging once they have satisfied the inclusion and exclusion criteria.. Once these have been satisfied, eligible patients will proceed to [¹8F]FPIA PET/MRI. The same treatment naiive patients, who have had one [¹8F]FPIA PET/MRI scan and completed SRS+/- combination therapy, may be invited to take part in a second [¹8F]FPIA PET/MRI scan, as long as they satisfy the inclusion and exlusion criteria.

On the day of imaging the patients will undergo a blood test to measure plasma concentrations of carnitine (approximately 6mls). During the scan, a single dose of [18F]FPIA (maximum, 370 MBq) IV will be administered to the participant followed by a whole brain dynamic PET/MRI scan over 66 minutes. During the MRI sequences, the patient will receive a 2 stage IV bolus of Gadolinium contrast medium administered through a peripheral venous cannula.

FPIA METS_PROTOCOL_V2.0_08APR2022

CONFIDENTIAL

6 PARTICIPANT ENTRY

A target of 24 evaluable subjects will be recruited. In the case of subject withdrawal or non-evaluable subjects before or after dosing, additional subjects will be enrolled to reach 24 evaluable subjects.

6.1 Identification and recruitment of subjects

Potentially eligible patients will be identified from the Imperial College Healthcare NHS Trust oncology multidisciplinary team meeting and from outpatient clinics by a members of the clinical and research team. The treating clinician will discuss the study with the patient at their clinic appointment and a patient information sheet explaining the study will be given to them or agreed to email or post to them either by the clinician or by a member of the clinical research team. Patients will be given a minimum of 24 hrs to consider participation in the study. After this time, they will be contacted by a member of the research team to discuss the study in more detail. Patients will then be invited to attend a screening up to 21 days before tracer administration and imaging.

[figure not shown]

Figure 2. Recruitment pathway

^{*}Treatment naïve or **SRS +/- combination therapy

6.2 Screening

Each patient will undergo screening assessments to confirm eligibility. Evaluations of the tumour and other clinical data obtained as standard of care prior to consent may be used for the study, provided they comply with the protocol specified timelines. Written informed consent will be obtained before the patient undergoes any study specific procedures.

Each potential patient will be assigned a unique identifier number for use during the trial. A complete record of all patients who enter screening for the study, as well as those who go on to be enrolled must be maintained at each site.

6.5 ID Assignment

Subject numbers will be assigned in successive order of inclusion.

7 STUDY PROCEDURES

The patient procedures are summarized in Table 1 below.

7.1 Schedule of Events

Table 1.

	Screening - 21 to day 0	Pre-PET/MRI day 0	[¹⁸ F] FPIA Dose	PET/MRI	
Informed Consent	•				
Entry Criteria	•				
Demographic Information	•				
Medical History	•				
WHO performance status	•				
Height and Weight		•			
Prior/Concomitant Medication ¹	•	•			
Blood test for renal function ²	•				
Carnitine blood test		•			
Pregnancy Test,3		•			
Vital Signs		•			
[¹⁸ F]FPIA injection			•		
Gadolinium contrast injection /kg (in 2 stages)				•	
Simultaneous PET/MRI Imaging*					\
Adverse events ⁴			•	•	•

- ¹ If screening and PET/MRI are on same day procedures do not have to be repeated.
- ² If result available from routine test within 90 days of [¹⁸F]FPIA injection, this does not need to be repeated (determined by investigator).
- ³ In women of child bearing potential prior to injection of imaging agent.
- 424-hour post scan Adverse Event reporting period.

7.2 Screening Period

Subjects will be screened up to 21 days before tracer administration to confirm eligibility.

Signed and dated informed consent must be obtained from all subjects prior to any protocol specific procedures being performed.

7.3 Screening Assessments

7.3.1 Demographic Data and Medical History

Demographic data and other characteristics will be recorded and will include date of birth, height, weight.

A standard medical history will be obtained including details of previous cancer medication, surgical history and tumour characteristics.

7.3.2 WHO Performance Status

Performance status will be assessed at the scheduled time points indicated in Table 1 according to WHO criteria as follows:

Table 2:

0	Fully active, able to carry on all pre-disease activities without restriction
1	Restricted in physically strenuous activity but ambulatory and able to carry out work of a light or sedentary nature. For example, light housework, office work
2	Ambulatory and capable of all self-care but unable to carry out any work activities. Up and about more than 50% of waking hours
3	Capable of only limited self-care, confined to bed or chair 50% or more of waking hours
4	Completely disabled. Cannot carry on any self-care. Totally confined to bed or chair
5	Death

7.3.3 Pregnancy Test

A urine pregnancy test will be performed prior to injection of imaging agent in women of child bearing potential.

7.3.4 Laboratory Evaluations

Blood samples for renal function may have been taken as standard of care in this patient population. Results of blood tests taken within 90 days of the scan can be used for study purposes. A new blood sample will be taken if a result is not available.

Blood will be taken for carnitine testing prior to the PET/MRI scan.

7.3.5 Concomitant Medications

Any concurrent, or procedural medications or therapy given to or taken by the subject from 2 weeks before inclusion into the study up to the end of the observation period will be recorded in the research notes.

7.3.6 Vital Signs

Blood pressure, pulse and temperature will be recorded.

7.3.7 Follow Up period

There is no PET/MRI related routine follow up. AEs will be reportable for up to 24 hours post scan. The patients will be assessed and followed up in all routine clinical procedures as per local policy by the treating clinician.

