8.1.3 Time on study

The last study related visit for a subject would be the PET/MRI scan. There are no follow up patient visits unless follow up for resolution of Adverse Events is required.

Depending on the screening period taken in relation to the scan day, a subject can be on study between 2 and 23 days including a 24 hour post scan reportable Adverse event period.

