9.2 Imaging Protocol

- Patients taking part in this study will have either one or two [18F]FPIA PET/MRI scans
- ¹⁸F-FPIA PET/MRI imaging will be carried out at the Hammersmith Hospital site, within Invicro.
- Pre-scan assessments will be carried out as per Table 1.
- A peripheral venous cannula will be inserted within the arm for radiotracer and MRI contrast injections.
- Simultaneous [¹⁸F]FPIA PET and MRI whole brain imaging (single bed position over the whole brain from vertex).
- Following completion of imaging, the venous cannula will be removed at the end of the scan and patient will be discharged.
- AEs will be reportable for up to 24 hours after the scan.

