10.2 Reporting of Adverse Events

10.2.1 Non serious AEs

AEs will be collected from the start of each scan visit to up to 24 hours after each PET/CT scan.

Any AEs which remain unresolved at the patient's last visit in the study should be followed up by the Investigator for as long as medically indicated.

Depending on the nature of the event the reporting procedures below should be followed. Any questions concerning adverse event reporting should be directed to the Chief Investigator in the first instance

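### AEs are to be collected up to 24 hours after each scan, but the plan gives no means of finding those that start after the patient is discharged at scan end

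*Combined protocol and SAP*

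**What the plan says.** The collection window is set in section 10.2.1: "AEs will be collected from the start of each scan visit to up to 24 hours after each PET/CT scan". The same 24 hours appear in footnote 4 of Table 1 and in sections 7.3.7, 8.1.3 and 9.2. Section 8.1.3 counts them as time on study: "a subject can be on study between 2 and 23 days including a 24 hour post scan reportable Adverse event period".

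What happens to the patient in that window is set elsewhere:

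- Section 9.2, at the end of imaging: "the venous cannula will be removed at the end of the scan and patient will be discharged".
- Section 8.1.3: "The last study related visit for a subject would be the PET/MRI scan", and then "There are no follow up patient visits unless follow up for resolution of Adverse Events is required".
- Section 7.3.7: "There is no PET/MRI related routine follow up. AEs will be reportable for up to 24 hours post scan". It continues: "The patients will be assessed and followed up in all routine clinical procedures as per local policy by the treating clinician".

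Section 10.2.1 also asks the investigator to follow any AE still unresolved at the patient's last study visit. Section 8.2 has the study team review safety data for trends and signals that would call for withdrawing a subject.

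**The concern.** The plan promises collection over a period in which it schedules no contact with the patient. If it is followed as written, the study team sees the patient through the scan and then has no planned way to learn of anything that starts later. The absence of a recorded AE after discharge could then mean either that nothing happened or that nobody asked.

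The protocol describes this as the first use of the tracer in patients with cerebral metastases (section 11.1), and each scan also involves a two-stage gadolinium injection (section 5.1). A short and simple safety record is reasonable for a single-dose imaging study, but it should cover the period that it claims to cover. Otherwise the review in section 8.2 works from incomplete data, and any statement about tolerability over 24 hours says less than it appears to.

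**Working it through.** **1. The plan's own figure.** Section 8.1.3 gives 2 to 23 days on study.

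- Maximum: 21 screening days (section 7.2) + 1 scan day + 1 day for the 24 hours = 23.
- Minimum: screening and scan on one day (1) + 1 day = 2.

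Both ends reproduce, so the 24 hours after the scan are counted as study time.

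**2. Is there a way to find new events in that time?** Each provision that might supply one was checked.

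| Provision | What it covers | Finds an AE that starts after discharge? |
|---|---|---|
| 7.1, Table 1 footnote 4 | names the 24-hour period | No; no call, visit or diary row |
| 7.3.7 | no routine scan-related follow-up; routine care continues | No study method; no stated route from routine care to the team |
| 8.1.3 | return visits to resolve AEs | No; the AE must already be known |
| 9.2 | discharge at scan end; 24-hour window repeated | No |
| 10.2.1 | AEs unresolved at the last visit | No; the last visit is the scan |

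Section 8.4 points the same way. It ends the study at the last patient's last visit, which by section 8.1.3 is a scan, so the final patient's 24-hour window falls after the defined end of study.

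**3. Share of the window after discharge.** Inputs: 66 minutes of scanning starting at injection (section 9.3), discharge at scan end (section 9.2), and 24 h = 1,440 min of window after the scan.

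- Window from injection = 66 + 1,440 = 1,506 min = 25.1 h.
- Share after discharge = 1,440 / 1,506 = 95.6%.

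Section 10.2.1 starts the window at the beginning of the visit, whose length is not given. If the visit lasts 2 to 4 hours (assumption), the share is 24/26 = 92% to 24/28 = 86%. These are shares of hours, not of events; the documents give no distribution of AE onset times.

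**4. What incomplete capture does to a clean record (illustration).** Let *a* be the share of AEs that reach the team. The documents do not give it, so a range is shown, with one scan per patient.

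- No AE recorded in 24 patients: the one-sided 95% upper limit for the recorded rate is 1 − 0.05^(1/24) = 11.7%. For the true rate it is 11.7%/*a*.
- Chance of recording at least one case in 24 patients, if the true rate is 10% (assumption): 1 − (1 − 0.10*a*)^24.

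| *a* | Upper limit with 0/24 recorded | Chance of at least one record at a 10% rate |
|---|---|---|
| 1.00 | 11.7% | 92% |
| 0.75 | 15.6% | 85% |
| 0.50 | 23.5% | 71% |
| 0.25 | 46.9% | 46% |

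**5. Number of scans.** There are 24 evaluable patients (12 + 12, section 5.1). Up to 12 treatment-naïve patients may have a second scan, giving 24 to 24 + 12 = 36. This is not a ceiling, because sections 6 and 8.1.2 replace subjects who are non-evaluable after dosing.

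**The case against.** The strongest reply is that silence about method is not a prohibition. Section 7.3.7 excludes only routine follow-up, section 8.1.3 excludes only visits, and section 10.2.1 says that AEs will be collected, which implies that someone will ask. A reader might infer that the plan forbids any later contact. It does not, and a telephone call would be compatible with most of the present text.

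A reader might also infer that a later AE comes to light only if the patient volunteers it. That goes too far. The treating clinician continues to see the patient and introduces the study (sections 7.3.7 and 6.1), and the GP is told of participation (section 12.9). Events may surface that way, although no section links these routes to AE recording.

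A third tempting inference is that the halting rule in section 8.3 is disabled. That rule responds to SAEs related to dosing. Section 10.2.2, which governs SAEs, puts no 24-hour limit on when they may occur, and nothing ties the rule to the AE window alone.

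Finally, safety is not among the endpoints in section 4.2 and section 11 plans no AE-rate analysis, so no planned estimate is biased. This stands, and it limits the consequence.

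Some material cannot be checked. Table 1 has an AE mark in a column without a legible heading, which may be a post-scan column; that would show the period, not the method. The consent pages and the CRF are not available and might carry reporting instructions.

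What remains after these points is that the protocol itself states no method for finding AEs between discharge and 24 hours.

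**Conclusion.** The point holds as a gap in ascertainment. The plan commits to collecting AEs for 24 hours after each scan, discharges the patient at scan end, states no routine scan-related follow-up, and provides follow-up only for AEs already known. About 24 of the 25.1 hours from injection (95.6%) are left without planned ascertainment, or 86% to 92% counted from the start of an assumed 2- to 4-hour visit. AEs that start in that time depend on unsolicited reports or on routine care.

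The effect is on the completeness of the safety record and on the review in section 8.2, not on any endpoint. The 95.6% assumes that the scan ends 66 minutes after injection and that discharge follows at once. The illustrated upper limits and detection chances depend on assumed capture shares and an assumed AE rate, and do not measure how many events would be missed. The change should be made because it is cheap and makes the existing commitment achievable. The documents do not support a claim that contact is forbidden or that the halting rule fails.

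**What to change.** Add to Table 1 and section 7.3.7 one telephone contact per scan, at or just after 24 hours, made by the existing research team, with a fixed AE question and the answer recorded on the CRF. Amend the statement in section 7.3.7 that there is no routine scan-related follow-up so that it agrees.

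The cost is one short call and one CRF line per scan: roughly 24 to 36 calls for 24 evaluable patients, depending on how many repeat scans are done, plus any for replaced subjects. No extra visit or procedure is needed.

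At the same time, section 10.2.1 should name PET/MRI rather than PET/CT. This is clerical, since sections 7.3.7 and 9.2 already tie the window to the scan that is performed.
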